**Study Product:** **Ferric Carboxymaltose (Injectafer) marketed by American Regent Inc. (Shirley NY)**

**Protocol Number:** **s17-00444**

**IND Number:** **IND Exemption Letter Requested**

## Study Summary

Title	Ferric Carboxymaltose To Improve Skeletal Muscle Metabolism in Heart Failure Patients with Functional Iron Deficiency
Short Title	FCM To Improve Sk. Muscle Metabolism in HF Patients with Fe Def.
Protocol Number	NYULMC IRB number: s17-00444
Phase	Phase 2 study of FDA-approved drug
Methodology	Double-blind, placebo-controlled single center randomized clinical trial
Study Duration	2 years
Study Center(s)	Single Center (NYULMC)
Objectives	To compare the effects of ferric carboxymaltose vs. placebo on skeletal muscle mitochondrial oxidative capacity, submaximal exercise tolerance, and health-related quality of life in HF patients with functional iron deficiency.
Number of Subjects	50 subjects will enrolled to identify 32 subjects eligible for randomization
Diagnosis and Main Inclusion Criteria	Clinically stable ambulatory chronic heart failure patients with functional iron deficiency without contraindication to study procedures (MRI and intravenous infusion of ferric carboxymaltose)
Study Product, Dose, Route, Regimen	Ferric carboxymaltose (Injectafer®) 750 mg intravenously, or normal saline (placebo)
Duration of administration	A single dose of ferric carboxymaltose or placebo will be administered.
Reference therapy	Placebo
Statistical Methodology	The change in the primary and secondary endpoints from baseline to week 4 will be compared between the two treatment arms by two-sided two sample t-test or Wilcoxon rank sum test. Significance will be decided at alpha=0.05.

[figure not shown]
## INTRODUCTION

**Statement of Compliance:** This trial will be conducted in accordance with the ICH E6, the Code of Federal Regulations on the Protection of Human Subjects (45 CFR Part 46), and the NHLBI Terms of Award. The Principal Investigator will assure that no deviation from, or changes to the protocol will take place without documented approval from the Institutional Review Board, except where necessary to eliminate an immediate hazard(s) to the trial participants. All personnel involved in the conduct of this study will have completed Human Subjects Protection Training and provided all required Conflict of Interests documentation before participation in research.

**Background and Significance:** Heart failure affects an estimated 6 million persons in the US, and is associated with high rates of hospitalization (1.1 million per year), high health care costs (>\$30 billion Medicare costs on an annual basis), and high mortality risk (30-50% over 5 years). The pathophysiology of heart failure is fundamentally determined by the failure of the circulatory system to deliver oxygen/nutrients sufficient for metabolic needs, and is best explained by a complex interplay between intrinsic abnormalities of myocardial contractile function and extra-cardiac factors that regulate oxygen utilization in metabolically active tissues. In patients with heart failure, reduced cardiac output reserve, impaired regulation of skeletal muscle blood flow, and abnormalities in skeletal muscle mass and mitochondrial function (e.g. reduced oxidative phosphorylation) all appear to be important determinants of exercise intolerance and may offer novel targets for therapy.

Iron is an essential trace element for oxidative metabolism. Many of the proteins responsible for oxygen transport to skeletal muscle (hemoglobin, guanylyl cyclase), oxygen storage (myoglobin) and oxygen utilization in skeletal muscle (cytochromes and iron-sulfur enzymes involved in electron transport in mitochondria) require iron as an essential co-factor for normal enzyme activity. Iron homeostasis is regulated by hepcidin, a liver-derived peptide hormone that modulates macrophage transfer of iron from enterocyte to the reticuloendothelial system by interaction with the iron channel protein ferroportin. Hepcidin secretion is modulated by metabolic sensors of tissue oxygen tension, and by inflammatory mediators such as interleukin-6 (Figure 1, adapted from ref 3). In patients with heart failure, chronic inflammation and hepatic congestion are associated with abnormal iron homeostasis characterized by increased hepcidin secretion and consequent functional iron deficiency with or without anemia. Functional iron deficiency is present in 35-50% of heart failure subjects and is associated with exercise intolerance and greater mortality risk in patients with concomitant anemia (HR 1.71, 95% CI 1.24-2.36, p=0.001) or without concomitant anemia (HR 1.44, 95% CI 1.11-1.87, p=0.006).

Two randomized clinical trials of the effects of intravenous iron on measures of functional capacity have been published. The Ferinject Assessment in Patients with Iron Deficiency and Chronic Heart Failure (FAIR-HF) study was a randomized, double-blind placebo-controlled trial that compared the effects of treatment with intravenous ferric carboxymaltose vs. placebo for 6 months on measures of functional capacity in 459 patients with symptomatic chronic heart failure, hemoglobin level 9.5-13.5 g/dl, and functional iron deficiency. Ferric carboxymaltose was administered weekly to achieve the replacement dose based on a clinically used formula, and then given every 4 weeks based on serial measurements of serum ferritin and transferrin saturation. When compared with placebo, subjects who received ferric carboxymaltose improve symptoms, improved 6-minute walk distance and improved quality of life after 6 months (all p<0.001). These benefits were consistent across pre-specified subgroups, including subjects without anemia, and subjects with higher than median serum ferritin at study entry. Intravenous iron therapy was well-tolerated, with no difference in study discontinuation or adverse events when compared with placebo. The CONFIRM-HF (FerricCarboxymaltOse evaluatioN on perFormance in patients with IRon deficiency in coMBination with chronic Heart Failure) study was another randomized, double-blind, placebo controlled trial that compared the effects of treatment with intravenous ferric carboxymaltose vs. placebo for 12 months on 6-minute walking distance in 304 patients with symptomatic chronic heart failure. The entry criteria and treatment regimens were similar to the FAIR-HF study, except the intravenous iron was given in doses ranging 500-750 mg via intravenous bolus. When compared with placebo, subjects who received ferric carboxymaltose demonstrated improved 6-minute walk distance (p<0.001), improved symptoms (p<0.001),

improved quality of life (all  $p=0.01$ ) and reduced hospitalization risk ( $p=0.009$ ) at 52 weeks of follow-up. These benefits were consistent across subgroups including subjects without anemia, and subjects with higher than median serum ferritin at study entry. Intravenous iron therapy was well-tolerated, with no difference in study discontinuation or adverse events when compared with placebo. Taken together, these two studies provide concordant evidence of improved exercise capacity in response to intravenous iron therapy even in patients without evidence of anemia.

## PRELIMINARY DATA

We measured post-exercise phosphocreatine recovery time as a validated index of skeletal muscle mitochondrial oxidative capacity with a novel spectrally selective three-dimensional turbo spin echo (3D-TSE) 31P MRS/MRI protocol developed at NYU School of Medicine in eight non-anemic HF patients and five non-heart failure control subjects. In three of the HF patients with functional iron deficiency, the 31P MRS/MRI protocol was repeated one week after a single dose of ferric carboxymaltose 500 mg. In agreement with previous studies using surface coils, we showed that the post-exercise phosphocreatine recovery time was prolonged in HF subjects when compared with control subjects (Figure 1), both for the whole muscle of the lower extremity (MRS Global and MRI Global) and also for individual muscle groups. In three HF subjects with functional iron deficiency, intravenous administration of ferric carboxymaltose 500 mg increased serum ferritin (mean 67 to 783 ng/mL), increased 6-minute walk distance (mean 342 to 369 m), decreased post-exercise phosphocreatine recovery time (mean 51 to 39 seconds, Figure 3), but did not change hemoglobin level (mean 14.6 to 14.0 g/dL). Intravenous iron was well-tolerated. There were no adverse events related to study drug or study procedures. These data were presented in abstract form at the 2015 International Society for Magnetic Resonance in Medicine meeting.

**Significance:** Abnormal iron homeostasis due to chronic inflammation and/or nutritional deficiencies affects over 1 billion persons worldwide. Functional iron deficiency is present in 50% of heart failure patients and is associated with more severe symptoms and greater risk for adverse outcomes with or without anemia. Although the effects of iron deficiency on erythropoiesis are well characterized, there are no existing human data on the impact of iron deficiency on skeletal muscle metabolism, and only limited data on the extra-medullary biological effects of intravenous iron therapy.

## STUDY OBJECTIVES

A single-center, prospective double-blind parallel group randomized study is proposed to compare the effects of ferric carboxymaltose vs. placebo on skeletal muscle mitochondrial oxidative capacity, submaximal exercise tolerance, and health-related quality of life in HF patients with functional iron deficiency. The goal of this study is to provide novel “proof-of-concept” data to demonstrate biological plausibility to support the use of ferric carboxymaltose in HF patients and other disease populations with functional iron deficiency.

32 eligible subjects will be randomly assigned (1:1) to ferric carboxymaltose 750 mg or placebo (normal saline) and will undergo serial assessment before and 4 weeks after study drug administration to address the following study endpoints:

**Primary Endpoint:** To compare the effects of ferric carboxymaltose 750 mg vs. placebo on change in skeletal muscle mitochondrial oxidative capacity from baseline to 4 weeks (post-exercise phosphocreatine recovery time measured non-invasively with 31P-magnetic resonance spectroscopy).

[figure not shown]

Figure 1. Mean $\pm$ SEM data for comparison of global (31P-MRS) and regional (31P-MRI, gastrocnemius medial (GM), gastrocnemius lateral (GL), and soleus muscle (SOL)) post-exercise PCr recovery time constant between 5 healthy control subjects (blue bars) and 8 HF subjects (red bars).

## Secondary Endpoints.

To compare the effects of ferric carboxymaltose 750 mg vs. placebo on:

- Change in 6-minute walk test distance from baseline to 4 weeks
- Change in Kansas City Cardiomyopathy Questionnaire score from baseline to 4 weeks
- Change in laboratory markers of iron stores and complete blood count from baseline to 4 weeks

## STUDY DESIGN

The proposed study design is a prospective, single-center, randomized, double-blind, parallel group placebo-controlled study (Figure 2). Primary and secondary endpoints will be assessed before and 4 weeks after administration of ferric carboxymaltose or placebo. It is anticipated that the study will require 2 years to complete enrollment.

**Study population:** Up to 50 subjects will be recruited from the clinical practice of the NYU Advanced Cardiac Therapeutics group at NYU Langone Medical Center. 36 eligible subjects will be randomized. Study entry criteria are listed in the Human Subjects section below.

**Study visits:** The study will require 3 visits over approximately 8-10 weeks for each subject: Visit 1: Screening; Visit 2: Baseline primary and secondary endpoint measurements, randomization, and study drug administration; Visit 3: final assessment of primary and secondary endpoint measurements. Additional details of the procedures at each study visit are described below.

**Study agent and control description:** Ferric Carboxymaltose (Injectafer®, 750 mg iron/15 ml sterile single use vial) will be provided by the American Regent pharmaceuticals (Shirley, NY) to the NYU Investigational Pharmacy and stored in the NYU Investigational pharmacy at 20°C to 25°C according to manufacturer instructions. An IND exemption will be requested from the FDA. Ferric carboxymaltose is nonionic polynuclear iron (III) hydroxide carbohydrate complex that binds iron tightly and requires macrophage processing for release of iron into body stores. Ferric carboxymaltose has been demonstrated to be safe and effective in the treatment of iron deficiency anemia and is FDA-approved for treatment of iron deficiency in adult patients. The most common adverse reactions recorded in clinical trials (>2%) are nausea, hypertension, flushing, hypophosphatemia, and dizziness. The dosing and route of administration used in this study protocol are consistent with the FDA-approved prescribing information for this drug (see appendix for FDA-approved package insert) and prior studies of this agent in heart failure populations.

**Study drug administration:** Intravenous ferric carboxymaltose 750 mg will be mixed under sterile conditions in 100 ml of normal saline for final concentration of 7.5 mg/ml and administered via volumetric infusion pump over 15 minutes. Placebo will consist of 100 ml of normal saline solution, and administered via volumetric infusion pump over 15 minutes. The research pharmacy will dispense study agent based on the randomized treatment allocation sequence.

**Study Agent blinding procedure.** Since ferric carboxymaltose is a dark brown solution, the study agent will be administered by un-blinded research nursing personnel of the NYU Clinical Translational Science Institute who are not otherwise involved in the research study procedures. A licensed physician safety monitor not otherwise involved in study procedures will be available to monitor the infusion procedure. Blinded research personnel will not be present during the study agent infusion. Opaque covers over the study agent infusion equipment and curtains will be used to maintain blinding for the study participants.

**Study Drug Randomization Procedure:** A variable size blocked randomization allocation scheme will be generated by an independent biostatistician and held by the NYU research pharmacy. When an eligible subject arrives at the research site for participation in study visit 2, a study drug order will be placed in the electronic medical record, and a randomization form will be hand-delivered to the NYU Investigational Pharmacy. The Investigational Pharmacist will confirm subject eligibility and assign the treatment allocation based on the sequence of the randomization code. The Investigational Pharmacist will process the study agent order in the electronic medical record, dispense assigned study drug to the un-blinded CTSI research nurse. Case report forms to track the treatment allocation for each participant (ID number and randomization code number) will be

[figure not shown]

Figure 2. Study design overview. FCM=ferric carboxymaltose

completed by the NYU investigational pharmacist, and verified by the unblinded CTSI research nurse assigned to administer study drug. Blinded research personnel will not have access to the randomization case report form. Except in case of emergency, treatment allocation will not be revealed to the investigation team until the last enrolled subject has completed all of the study procedures and the database is locked.

**Medical History:** The following information will be obtained from review of the medical record and/or patient interview at Visit 1: 1) Left ventricular ejection fraction (date and imaging mode); 2) Etiology of heart failure (ischemic or non-ischemic); 3) Duration of heart failure (years); 4) NYHA Class (I-IV); 5) Co-morbid diseases (hypertension, hyperlipidemia, coronary artery disease, chronic kidney disease, chronic lung disease, atrial fibrillation); 6) Medications by pharmacological class: angiotensin converting enzyme inhibitors, angiotensin receptor blockers, beta-adrenergic receptor blockers, digitalis glycosides, loop diuretics, mineralocorticoid receptor antagonists, statins, aspirin, thienopyridines, warfarin, and novel oral anticoagulant agents; 7) Demographic information including age, sex, ethnicity; 8) Contact information including home, work and mobile phones, street address, email address (to be purged after completion of study visits).

**Heart Failure Symptoms:** The following information will be obtained from review of medical record and/or patient interview: 1) Functional capacity; 2) Orthopnea, paroxysmal nocturnal dyspnea, edema; 3) Medical resource use (doctor visit, emergency department visit, hospitalization); 4) Medication change; and 5) Use of appropriate measures to protect against pregnancy in women of childbearing potential.

**Cardiovascular examination:** Limited physical examination to assess evidence of congestion including assessment of jugular venous pressure, lung exam, cardiac exam, abdominal exam for hepatomegaly, and extremity exam for edema and perfusion.

**Safety Blood Monitoring:** Venous blood will be collected from a forearm vein with standard sterile venipuncture technique for analysis of biomarkers of iron stores (serum iron, total iron binding capacity, serum ferritin), complete blood count, comprehensive metabolic panel, serum phosphate, and beta-HCG (for women of childbearing potential) according to the schedule of assessments (Table 1). All laboratory analyses will be performed by the New York State licensed CLIA-compliant NYU Langone Medical Center Tisch Hospital Clinical Laboratory.

**Kansas City Cardiomyopathy Questionnaire.** The KCCQ is a self-administered disease-specific health status instrument composed of 23 items that quantify the domains of physical limitation, symptoms, self-efficacy, social limitation, and quality of life limitation from heart failure. Participants will complete the questionnaire form under the supervision of the research staff. The questionnaires will be scored by an automated system provided by the distributor of the questionnaire.

**Six-minute walk test:** The 6-minute walk test is a validated quantitative measure of functional capacity in patients with heart and lung diseases. This submaximal self-paced test will be conducted according to

American Thoracic Society guidelines at Visits 1 and 2. Subjects will be asked to walk along a 30 meter marked path in a corridor at a self-selected pace. Subjects will receive standardized instruction before and during the walking test. The distance walked after 6 minutes (meters) will be recorded.

**31P-MRS and MRI protocol:** We will use a spectrally selective three-dimensional turbo spin echo (3D-TSE) protocol for measurement of phosphocreatine recovery kinetics on a 3T Siemens MRI scanner as previously described (Siemens Medical Solutions, Erlangen, Germany). Each subject will perform the same rhythmic plantar extension exercise protocol twice, for sequential acquisition of MRS and MRI measurements respectively. For the exercise protocol, the subject will lay supine on the scanning table with the right leg inside the volume coil. The exercise consists of repeated plantar flexion movements using resistance bands at a frequency of one repetition per second for 1-2 minutes. Data are collected continuously for 2 minutes before the exercise (baseline), during exercise, and 5 minutes after the exercise for the MRS and MRI experiments. The phosphocreatine recovery kinetics will be calculated as previously described.

**Ankle brachial index.** Systolic blood pressure in the brachial artery and in the posterior tibialis artery or dorsalis pedis artery will be determined with a Doppler ultrasound flow probe. The ankle brachial index is calculated as the ratio of the ankle:arm pressures.

**Adverse Event Monitoring:** The Principal Investigator is responsible for monitoring and reporting adverse events to the ethical review board. The definitions and procedures for classification and reporting of adverse events (AEs) are described in the Human Subjects section below. Subjects will be prompted to report any new problems or events since the start of the study at each visit.

**Early Withdrawal Criteria:** Subjects may be removed from participation based on the following criteria: subject request, intolerance of study drug or study procedures, intercurrent illness that alters risk of participation or interferes with study procedures, acquisition of new information that affects subject eligibility (e.g. pregnancy or prohibited concomitant medication), or other situations that would put the subject at increased risk, compromise adherence to study procedures, or confound interpretation of the study findings. Women of childbearing potential will be instructed to use accepted methods of contraception to avoid pregnancy during the study, and will have a blood pregnancy test at screening, and before all study visits with efficacy endpoint assessments.

**Early study termination criteria:** The study may be prematurely terminated or suspended by the Principal Investigator due to issues related to participant safety, study futility, failure to meet accrual, site performance, or data quality and completeness milestones, failure to adhere to ethical standards in the conduct of human subjects research, or other study protocol deviations.

## DATA ANALYSIS

**Data management and analysis:** All data will be recorded on paper case report forms as primary source documentation and will be transferred to a secure REDCap electronic database protected by the NYU firewall. Case report forms and electronic data will use a randomly assigned Study ID number and will not include any identifiers. A separate study folder with study subject contact information will be kept in a locked cabinet in a locked room. PHI for each subject will be securely destroyed after completion of the study visits.

**Hypothesis to be tested:** The null hypothesis to be tested is that there is no difference between ferric carboxymaltose and placebo for the change in the primary and secondary study endpoints over 4 weeks.

### Description of analysis sets:

Efficacy analysis dataset. Intention to treat (ITT) will be defined as all patients who have been randomized to study treatment and completed at least one follow-up visit with primary endpoint data collection. The ITT data set will be used for the primary and secondary efficacy endpoints and ancillary study endpoints.

Safety analysis dataset. All patients who received study drug, and for whom post-dose data are available, will be included in the safety analysis set.

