### Analysis plan for primary and secondary endpoints:

The objective is to compare the change in the primary and secondary endpoints over time between the two treatment groups.

Descriptive analysis techniques will be used to characterize study participants. Center and variability of continuous variables will be presented as means (SD) when they follow a normal distribution and as medians and interquartile range otherwise. Log transformation will be applied on variables with skewed distribution.

The primary endpoint is change in the phosphocreatine recovery time (s). Secondary endpoints are 1) change in six-minute walk distance (m), change in quality of life score (points), and change in hemoglobin (g/dL), serum ferritin (ng/ml), and transferrin saturation (%). The change in the primary and secondary endpoints from baseline to week 4 will be compared between the two treatment arms by two-sided two sample t-test or Wilcoxon rank sum test. Significance will be decided at alpha=0.05.

We will also construct multivariable regression models with treatment assignment as the main predictor and the change in the primary or secondary endpoint as the outcome variable while adjusting for patients' characteristics such as baseline value of the endpoint, age, sex, ethnicity, hemoglobin level, and measures of disease severity and their interactions with the treatment assignment if necessary. Pre-specified subgroup analyses are based on median age, sex, heart failure etiology (ischemic vs. non-ischemic), NYHA functional Class, median serum ferritin level, and sex-stratified median hemoglobin level.

**Missing Data Consideration:** We anticipate a low percentage of missing data due to the short duration of the study and relatively small data set. The missing data will be handled by intent-to-treat analysis in principle, with last value carried forward. We will compare baseline data in subjects with and without missing data to identify factors contributing to missingness. As sensitivity analyses, a "per protocol" analysis, and analysis with multiple imputation will be undertaken with five imputed datasets using the NORM software. Parameter estimates and their standard errors will be derived by averaging across the five imputations and by adjusting for their variance.

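### The efficacy set labelled ITT holds only patients seen at Visit 3, and the last-value-carried-forward rule conflicts with it and can carry only pre-dose values

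*Combined protocol and SAP*

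**What the plan says.** All references are to the combined protocol and SAP.

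- **Description of analysis sets.** The ITT set is those "randomized to study treatment and completed at least one follow-up visit with primary endpoint data collection". The same set serves the primary, secondary and ancillary efficacy endpoints.
- **Study Design, study visits.** There are three visits: screening; baseline measurement with randomisation and dosing; and "Visit 3: final assessment of primary and secondary endpoint measurements". Study Objectives and Table 1 agree that efficacy is measured once after dosing, at 4 weeks. No early-withdrawal efficacy visit is described.
- **Missing Data Consideration.** "The missing data will be handled by intent-to-treat analysis in principle, with last value carried forward". Little missing data is expected. "We will compare baseline data in subjects with and without missing data to identify factors contributing to missingness". As sensitivity analyses there is a per-protocol analysis, and "analysis with multiple imputation will be undertaken with five imputed datasets using the NORM software". The set for the imputation is not named.
- **Primary test.** Changes to week 4 "will be compared between the two treatment arms by two-sided two sample t-test or Wilcoxon rank sum test".
- **Sample size calculation, Table 2.** 16 per group with no dropout, 13 per group at 4 weeks with 20% dropout.

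**The concern.** An intention-to-treat label tells the reader that every randomised patient is counted in the assigned arm. Here membership depends on something that happens after randomisation: reaching Visit 3 with primary endpoint data collection. Treatment is a single dose, so withdrawal affects the analysis only through a missed Visit 3. The Early Withdrawal Criteria do, however, allow removal for drug intolerance or intercurrent illness, and such losses could differ by arm.

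The missing-data rule does not repair this. It speaks of intention-to-treat, yet those who miss Visit 3 have already been excluded. If an analyst restores them in order to follow the rule, the only scan available to carry is the pre-dose one. The reported effect would then depend on which paragraph was followed.

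The set definition also leaves open whether attendance is enough or a usable scan is needed. If a scan is needed, one failed scan removes that patient's walk distance, questionnaire and laboratory results from the efficacy analysis.

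**Working it through.** **Inputs.** From Sample size calculation and Table 2: 16 per arm, 0–20% dropout, a 10 s change called likely meaningful, SD up to 8 s, two-sided alpha 0.05. Assumed, because the documents give no figure: how losses split between arms, and the mean change on placebo.

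**The plan's own figures.** Detectable difference in SD units at 90% power, normal approximation: (1.960 + 1.282) × √(2/n).
- n = 16: 1.146 (Table 2: 1.15).
- n = 13: 1.271 (Table 2: 1.3).

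Table 2 reproduces. Since 16 × 0.8 = 12.8, rounded to 13, the upper dropout limit is 3 lost per arm. Table 2 therefore also leaves dropouts out of the analysis.

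**What LOCF can carry.** There is one post-dose efficacy assessment per endpoint. If it is missing, no post-dose value exists. There are three cases:
- A non-attender restored to the analysis: the baseline scan is carried, change = 0.
- A secondary value missing for a patient inside the set: a pre-dose value is carried, change = 0.
- An unusable Visit 3 scan, if attendance alone qualifies: the baseline scan is carried, change = 0. Here LOCF acts on the primary endpoint inside the set.

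**Dilution.** With m of N lost per arm, loss unrelated to outcome and no placebo change, the expected LOCF difference is 10 × (N − m)/N.

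| Lost per arm | N = 16 | N = 18 |
|---|---|---|
| 1 | 9.4 s | 9.4 s |
| 2 | 8.75 s | 8.9 s |
| 3 | 8.1 s | 8.3 s |

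The N = 18 column is there because Study Design says "36 eligible subjects will be randomized", while the Study Summary and Study Objectives say 32. The two need reconciling. With 3 of 16 lost, the shrinkage is 3/16, about 19%.

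**Power.** Simulation with 100,000 replicates, normal changes, two-sample t-test, true effect 10 s, 3 of 16 lost per arm:
- SD 8: completers 0.864, LOCF 0.846.
- SD 6: completers 0.983, LOCF 0.977.

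**Type I error of LOCF on all randomised patients.** No treatment effect, the same assumed improvement in both arms, 0 lost in one arm and 3 of 16 in the other:

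| Assumed improvement | SD 4 | SD 6 | SD 8 |
|---|---|---|---|
| 5 s | 0.087 | 0.067 | 0.061 |
| 2.5 s | 0.061 | 0.053 | 0.052 |
| 1 s | 0.050 | 0.051 | 0.051 |

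At 5 s the false difference is 5 × 3/16 = 0.94 s, in favour of the arm with fewer losses. Also at 5 s, losses of 0 vs 1 or 1 vs 3 give 0.050 to 0.052, and 3 vs 3 gives 0.022 to 0.040, below the nominal level.

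**The case against.** The strongest reply is that the plan does indicate what it intends. The set definition is assigned explicitly to the primary and secondary endpoints, and Table 2 counts 13 per group at 4 weeks. Both point to analysing those seen at Visit 3, and the LOCF sentence is qualified as holding in principle. This stands. A reader might infer that the plan offers two equally supported analyses; it does not. It has a set definition and a missing-data rule that disagree, with most of the text favouring the former.

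The second reply is that the effect is small. Little missing data is expected, the 8.1 s figure sits at the top of the dropout range, and power changes by about 0.02. This also stands.

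Third, a reader might infer that the completer comparison is itself biased. It is unbiased if loss is unrelated to outcome, and nothing in the documents shows otherwise. As an extreme bound, losing exactly the three least-improved treated patients would raise 10 s to between 11.2 s (SD 4) and 12.5 s (SD 8), but the plan gives no reason to expect that pattern.

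The planned safeguards answer only part of the point. The comparison of baseline data can reveal imbalance on measured factors. It cannot correct the label or the LOCF rule. The multiple imputation could cover everyone randomised, but the plan does not say so.

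**Conclusion.** The point holds as an inconsistency with a modest numerical effect. The set called ITT excludes randomised patients on a post-randomisation event, and the LOCF rule attached to it can only impute no change. That part follows from the visit schedule and needs no assumption.

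The size does rest on assumptions. A true 10 s becomes an expected 8.1 s under LOCF with 3 of 16 lost per arm, equal loss unrelated to outcome and no placebo change; it becomes 9.4 s or 8.75 s with 1 or 2 lost. It would be tempting to claim a serious loss of power or an inflated false-positive rate. The figures do not support either as a general statement. The power difference is about 0.02 at the largest SD in Table 2. Type I error reaches 0.06 to 0.09 (SD 8 to 4) only with 0 vs 3 losses and an assumed 5 s improvement in both arms, and stays at about 0.05 with 1 s. The change should be made before the data are unblinded, but the design does not depend on it.

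**What to change.** 1. Define ITT as all randomised patients, analysed by assigned arm. Rename the present set completers, and state whether it requires a usable scan or only attendance at Visit 3.
2. Delete LOCF.
3. State that the primary comparison uses observed week-4 change by assigned arm under a missing-at-random assumption. For an unadjusted test this means that, within each arm, loss is unrelated to the change. Report the numbers randomised and analysed per arm.
4. Run the already planned multiple imputation on all randomised patients with a small model: arm and baseline, plus an observed week-4 secondary value where only the scan is missing.
5. Analyse each secondary endpoint in every patient who has it, whether or not the scan succeeded.

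Keep the planned baseline comparison and per-protocol analysis. A delta-shift sensitivity analysis for outcome-related loss is optional in a trial of this size. Whether the primary test should adjust for baseline is a separate question.

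The cost is SAP wording and slightly more analysis work, with no added patients or procedures. The imputation standard error may be slightly larger than that of baseline-adjusted completers: about 3% in one simulation with 3 of 16 lost per arm (1.57 vs 1.52 s at SD 4; 3.12 vs 3.03 s at SD 8). That figure rests on an assumed baseline of 50 s (SD 10) and a baseline–change correlation of 0.3, and should be read as indicative only.
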